### Dose escalation strategy

Study product will be started at 5 mg/kg/day and increased every 3 days by 2.5 mg/kg/day to 10 mg/kg/day. Then increase the dosage every 5 days by 5 mg/kg/day until the subject reaches a maximum targeted dose (20 mg/kg/day) or experiences intolerable adverse effects, in which case the dose will be dropped to the last tolerated dose, for 10-15 days. Tolerability will be assessed on the third day of each dose between 5-10 mg/kg/day and the fifth day of each dose between 10-20 mg/kg/day and the subject is instructed whether or not to change the dose starting the next day. Once a subject has been on a specific dose for at least 3 days (5-10 mg/kg/day) or 5 days (10-20 mg/kg/day), that dose can be changed for less or more than 3 (5-10 mg/kg/day) or 5 days (10-20 mg/kg/day) and can be changed by a smaller increment (2.5-5 mg/kg/day) as needed for tolerability. The maximal tolerated dose is determined by the PI or co-Investigator that is an MD, based on their clinical expertise.

### Assessment of tolerability of each dose level

Tolerability will be assessed at each dose via collection of adverse events during administration of the standardized phone script by appropriate study staff. Severity of adverse events will be graded according to the Common Terminology Criteria for Adverse Events (CTCAE), which is published by the National Cancer Institute (NCI) of the National Institutes of Health (NIH):

Grade 1: Mild; asymptomatic or mild symptoms; clinical or diagnostic observations only; intervention not indicated.

Grade 2: Moderate; minimal, local or noninvasive intervention indicated; limiting age-appropriate instrumental ADLs. Instrumental ADLs refer to preparing meals, shopping for groceries or clothes, using the telephone, managing money, etc.

Grade 3: Severe or medically significant but not immediately life-threatening; hospitalization or prolongation of hospitalization indicated; disabling; limiting self care ADLs. Self care ADLs refer to bathing, dressing and undressing, feeding self, using the toilet, taking medications, and not bedridden.

Grade 4: Life-threatening consequences; urgent intervention indicated.

Grade 5: Death related to AE.

The protocol for dose adjustments, maintenance and discontinuation based on adverse effects is as follows:

- For subjects with a grade 1 adverse event the dose will be increased by up to 5 mg/kg/day, or if they are on the maximal targeted dose (20 mg/kg/day) it will be continued.
- For subjects with a grade 2 adverse event the dose will be reduced by 5 mg/kg/day or less.
- For subjects with a grade 3 or 4 adverse event that the Investigator determines is unrelated, the dose will be continued. When the adverse event is stabilized or resolved, e.g., subject is stable after a hip fracture repair, the dose will be increased unless they are already on the maximum targeted dose.
- For subjects with a grade 3 or 4 adverse event that the Investigator determines is related the study drug will be stopped and not restarted.

The Investigator will determine relatedness as described in Section IV. C.8, and will consider the adverse event related if she determines there is at least a reasonable possibility.

The major dose limiting effect, per GW, is somnolence. To monitor for this closely, the daytime sleepiness part to the SCOPA-sleep will be administered during each phone call, thus before each increase in dose. A score of >7 (note that the average score for PD is  $5.2 \pm 4$ ), if greater than before and considered problematic by the appropriate clinical staff, would result in the subject being instructed to drop to the prior dose for three more days before increasing the dose.

Additional assessments of safety and tolerability is done at the study visit when the subject is on the maximum tolerated or targeted dose. The same protocol for dosing is applied for both adverse events found during phone assessments and during study visits.

The results of safety and tolerability assessments in Stage 1 will be studied to determine if additional evaluations during Stage 2 are warranted. For example, if grade 1 or 2 adverse events occur in  $\geq 2$  subjects then additional surveillance will be conducted during Stage 2. Further, safety and tolerability Stage 1 results determine participant and study stopping parameters, described in Section IV C.7.

The CTCAE criteria are used to determine dose level adjustments and for participant and study stopping rules (Section IV C.7). Adverse events for both Stage 1 and 2 will be collected and reported as discussed in Section IV C.8.

To mitigate potential risk during the study, the subjects will be told not to drive cars or operate dangerous machinery while taking study drug in the Open Label Dose Escalation Tolerability study (Stage 1). Instructions to subjects in the Randomized Controlled Trial (Stage 2) will be developed after Stage 1 is completed, with COMIRB guidance.

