## IV. Research Methods

### A. Outcome Measure(s):

#### **Stage 1: Open Label Dose Escalation Tolerability Study**

**Primary Specific Aim:** To confirm that the dosage regimen of CBD, in the form of Epidiolex recommended by the study drug manufacturer is safe and tolerated in 10 subjects with PD. Epidiolex is started at 5 mg/kg/day and is increased every 3 days by 2.5 mg/kg/day to 10 mg/kg/day. Then increase the dosage every 5 days by 5 mg/kg/day to a target dose of 20 mg/kg/day.

**Primary Outcome Measures:** The safety and tolerability of Epidiolex is measured in 4 ways:

1. By examining the frequency of study-related adverse events at each dose level.  
Adverse events are measured primarily by a standardized phone script administered at each dose level. The phone script starts with an open ended question (Do you notice any effects, good or bad, of the study drug?) and followed by a series of yes/no questions regarding adverse effects (including previously reported adverse effects of CBD and general common adverse effects of medications), and all the effects we hypothesize in the study. For each adverse and beneficial reported effect, further questions will be asked, such as when did the effect start and how is it progressing, etc. In addition, since a major dose limiting effect, per GW, is somnolence, the daytime sleepiness part of the SCOPA-sleep is included in the phone script.

The phone script is administered before each dose increase. This phone call is done by a RN, MD or an advanced practice practitioner (APP). Tolerability is judged by the appropriate clinical staff (APP, neurologist) under the supervision of the PI and sub-I (who are MDs), based on their clinical expertise.

2. By monitoring vital signs, orthostatic blood pressures, physical exam, EKG and labs (hematology, complete metabolic profile, and urinalysis) during study visits.
3. By conducting standardized assessment tools on cognition, anxiety, psychosis, sleep, daytime sleepiness, mood, fatigue, pain, impulsivity, suicidality, and motor and non-motor PD signs during study visits. In addition, since many patients with PD also have restless legs syndrome and REM sleep behavior disorder, assessments for these are also done. The assessment tools are:

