10) population with severe epilepsy. Subjects were evaluated after 12 weeks on study drug, mean dose of ~23 mg/kg/day. Adverse events were reported in 128 (79%) of the 162 patients within the safety group. Adverse events reported in more than 10% of patients were somnolence (25%), decreased appetite (19%), diarrhea (19%), fatigue (13%), and convulsion (11%). Somnolence and fatigue were not dose related, diarrhea and weight loss occurred more often in subjects taking >15 mg/kg/day. Of note, the concomitant use of clobazam (an anticonvulsant medication) was highly associated with somnolence, meaning somnolence was less in those not on clobazam (21%) compared to those taking it (51%). Most adverse events were moderate and transient. SAEs deemed related to the study drug occurred in 12% of subjects, including 9 who had status epilepticus. However, of note, the study showed a ~50% reduction in seizures on study drug, and status epilepticus is a common problem in the population studied. Five subjects (3%) stopped the study drug due to an adverse event. Please see the article regarding clinically significant changes in safety blood analyses. Hepatotoxicity (< 1%), hyperammonemia (<1%), and thrombocytopenia (<1%) occurred only in subjects also taking valproate.

The maximum tolerated doses, in mg/kg/day, of the 10 subjects will be averaged, and adjusted to the next highest 5 mg/kg/day. That dose will be used as the targeted dose for the RCT. For example if the average of the maximal tolerated doses in Stage 1 subjects is 17.4 mg/kg per day, the targeted dose in the RCT will be 20 mg/kg/day. Or if the average of the maximal tolerated doses in stage 1 subjects is 22.7 mg/kg per day, the targeted dose in the RCT will be 25 mg/kg/day.

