## Schedule of Event- Stage 1 note

Note: regarding the rows of days and weeks, it is variable, because of note k and also because some patients will take shorter or longer to get to their maximum tolerated dose than those that titrated to 20 mg/kg/day.
a. A complete medical history (including PD history, mental health history, alcohol and drug use) will be obtained from the subject at the Screening Visit and recorded on the appropriate CRF. The medical history and other enrollment criteria will be reviewed and updated at the Baseline/Day 1 visit to determine continued eligibility for the study.
b. Adverse events will be recorded from the time of the first dose of study drug. Any subject with an ongoing AE will be followed until the AE is resolved, returns to baseline or deemed stable by the investigator.
c. Vital signs obtained after the subject has been sitting for at least 5 minutes. Body temperature will be obtained at screening, Day 1, and at the final follow up visit. Blood pressure, respiratory rate and heart rate will be measured once each day assessed. During screening only, after the seated blood pressure has been obtained, the blood pressure will be repeated within 3 minutes of the subject standing up. This procedure may be repeated, if appropriate, following hydration. If repeated, a total of two additional pairs of BP assessments (sitting/standing) should be obtained, and the results of the last attempt should be reported.
d. Complete PE to include: skin, head-neck, eyes-ears-nose-throat, lungs-chest, heart, abdomen, extremities, neurological.
e. Hematology consists of hemoglobin, hematocrit, mean corpuscular volume (MCV), mean corpuscular hemoglobin concentration (MCHC), red blood cell count (RBC), white blood cell (WBC) count, WBC differential (absolute), and numerical platelet count.
f. Serum chemistry (fasting not required) consists of alkaline phosphatase, albumin, blood urea nitrogen, calcium, carbon dioxide, chloride, creatinine (MDRD formula for eGFR, to be done by the central laboratory), $\gamma$ -glutamyltransferase, glucose, inorganic phosphorus, potassium, alanine aminotransferase, lactate dehydrogenase, aspartate aminotransferase, sodium, total bilirubin, and total protein.

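### The Stage 1 dosing rule cuts the dose for any grade 2 event, related or not, while an unrelated grade 3 or 4 event leaves the dose unchanged

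*Combined protocol and SAP*

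**What the plan says.** The dose-adjustment list is in IV.C.2 under Assessment of tolerability of each dose level. For grade 2 it says: "For subjects with a grade 2 adverse event the dose will be reduced by 5 mg/kg/day or less". Two further bullets divide grade 3 and 4 events by cause. For the unrelated ones, "For subjects with a grade 3 or 4 adverse event that the Investigator determines is unrelated, the dose will be continued", and the dose goes up once the event has settled, unless the subject is already at the maximum. For the related ones, the drug is stopped for good. After the list, the protocol says how the Investigator judges cause: she "will consider the adverse event related if she determines there is at least a reasonable possibility".

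The list covers the whole of Stage 1: "The same protocol for dosing is applied for both adverse events found during phone assessments and during study visits".

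Three other places matter:

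- IV.A gives the first Stage 1 tolerability measure: "By examining the frequency of study-related adverse events at each dose level".
- IV.C.2, Dose escalation strategy: "The maximal tolerated dose is determined by the PI or co-Investigator that is an MD, based on their clinical expertise".
- IV.C.1: the maximum tolerated doses "of the 10 subjects will be averaged, and adjusted to the next highest 5 mg/kg/day", and the result is the Stage 2 target.

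**The concern.** Stage 1 is meant to find what dose of the drug these patients tolerate. A reduction made for a cause unrelated to the drug carries no information on that question. The grade 2 bullet nevertheless requires the reduction, and the same list allows dosing to continue through an unrelated life-threatening event. The less severe event therefore has the larger consequence for the dose.

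Two things are at stake. The subject's own exposure is lowered, or at least delayed. If the dose is not raised again, the lower value may be recorded as the maximum tolerated dose and enter the average that fixes the Stage 2 target. Staff who see that the instruction makes little sense can only follow it or depart from it, and may not do so in the same way for every subject. The point does not extend to power, the tremor analysis or subject safety.

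**Working it through.** **Step 1. The text.** The Stage 1 actions, side by side:

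| Event | Judged related | Judged unrelated |
|---|---|---|
| Grade 2 | Reduce by up to 5 mg/kg/day | The same; cause is not mentioned |
| Grade 3 or 4 | Stop, do not restart | Continue; escalate once settled |

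Could other wording supply the missing condition? The sentence introducing the list speaks of adverse effects, which might suggest drug-caused events only. It also introduces the bullet on unrelated events, so it cannot confine the list to related ones. The sentence on reasonable possibility says how relatedness is judged, and among the dose bullets only those for grades 3 and 4 use that judgement. No other section exempts an unrelated grade 2 event.

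**Step 2. Inputs for the size of the effect.**

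- Ten subjects, averaged, then moved up to the next 5 mg/kg/day (IV.C.1).
- Stage 1 maximum 20 mg/kg/day; steps of 5 every 5 days between 10 and 20, and of 2.5 every 3 days below 10 (IV.C.2).
- Size of cut *c*: 5 or 2.5 mg/kg/day. The bullet allows anything up to 5.
- Number of subjects cut for an unrelated grade 2 event and never raised again, *k*: not in the documents, so varied.

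**Step 3. The rounding rule.** With *M* the ten-subject mean, the target is *T* = 5 × ceil(*M*/5), taking a mean that is an exact multiple of 5 as unchanged. This reproduces both of the protocol's examples: 17.4 gives 20, and 22.7 gives 25.

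**Step 4. Shift in the mean.** Each affected subject lowers *M* by *c*/10, which is 5/10 = 0.5 or 2.5/10 = 0.25. The observed mean is *M* − *kc*/10.

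**Step 5. When the target falls from 20 to 15.** This needs 15 < *M* ≤ 15 + *kc*/10:

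| *k* | Highest true mean affected, *c* = 5 | Highest true mean affected, *c* = 2.5 |
|---|---|---|
| 1 | 15.5 | 15.25 |
| 2 | 16.0 | 15.5 |
| 3 | 16.5 | 15.75 |

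**Step 6. Two reference cases.**

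- True mean 17.4, cuts of 5: four give 17.4 − 2.0 = 15.4, target 20; five give 14.9, target 15.
- True mean 17.4, cuts of 2.5: nine give 17.4 − 2.25 = 15.15, target 20; ten give 14.9, target 15.
- All ten would otherwise reach 20: nine cuts of 5 give 15.5, target 20; ten give 15.0, target 15. Ten cuts of 2.5 give 17.5, target 20.

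**Step 7. If the subject is re-escalated.** The loss is about one dose step: 5 days between 10 and 20 mg/kg/day, 3 days below 10. The maximum tolerated dose need not change. The Appendix 1 note on Stage 1 leaves room for this, since "some patients will take shorter or longer to get to their maximum tolerated dose than those that titrated to 20 mg/kg/day".

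**The case against.** The strongest reply is that the rule is deliberate caution. Cause is examined only where the consequence is irreversible, so that an event such as a hip fracture does not end participation. A grade 2 reduction is small and can be undone. Reducing on any moderate event is defensible in a population for which the protocol says the dose is not established. The wording on adverse effects, both before the list and in the escalation rule, suggests the authors had drug-caused events in mind. The reasonable-possibility standard leaves few grade 2 events that would be called unrelated. A physician sets the maximum tolerated dose, and the Stage 2 target is only a ceiling, because each subject is titrated as tolerated. Nor must a dosing rule match the scope of an outcome count.

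Much of this stands as a limit on size. Clearly unrelated grade 2 events may be uncommon, a physician can correct the recorded dose, and re-escalation is not barred. The mismatch with the IV.A measure is supporting context and would not show an error by itself.

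The caution argument does not explain the rule. Avoiding permanent withdrawal needs only an exemption from stopping, yet the list keeps the full dose through an unrelated grade 4 event and then raises it. A protocol that accepts this has no stated reason to cut for an unrelated grade 2 event. Where it wants the dose raised again it says so, both for unrelated grade 3 or 4 events and in the daytime-sleepiness rule. The grade 2 bullet is silent. Physician discretion over the maximum tolerated dose does not cancel a reduction that the list makes mandatory.

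**Conclusion.** The concern holds, as a minor one. The Stage 1 list gives an inconsistent instruction: an unrelated grade 2 event lowers the dose and an unrelated grade 3 or 4 event does not. The certain consequence, if the list is followed, is a lower dose for a time in the subject concerned. A lower recorded maximum tolerated dose is possible but not certain.

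An effect on the Stage 2 target requires unrelated grade 2 events, no re-escalation, no correction by the physician, and a true mean close above 15. The calculation assumes one cut per affected subject and rounding up as in the protocol's examples. The number of affected subjects is an assumption throughout.

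**What to change.** Limit the grade 2 reduction to events the Investigator judges related, using the reasonable-possibility standard already in the section. Then add a sentence for the remaining grade 2 events, in line with the rule for unrelated grade 3 and 4 events. Suggested wording: *Grade 2, judged related: lower the dose by up to 5 mg/kg/day. Grade 2, judged unrelated: keep the dose as it is, and resume escalation when the event has stabilized or resolved.*

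The cost is one amended bullet and one added sentence. No new data are needed, since relatedness is already assessed for adverse events under IV.C.8, Relationship to Study Drug. There are three small costs in practice:

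- A judgement on cause must be made before the next-day dose instruction. The grade 3 and 4 bullets already require one, and physicians already supervise the tolerability decisions.
- Escalation pauses until an unrelated grade 2 event settles, so some time can still be lost.
- There is slightly less caution for events judged unrelated. Events that could be drug or disease, such as fatigue or gait disturbance, would still count as related and lead to a reduction.

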#### Procedures at each visit

Visit 1-Screening visit: Consent, demographics, family medical history, concomitant medications, formal drug interaction assessment, vital signs, orthostatic blood pressures, history & physical examination (complete physical exam and detailed neurological exam), tremor evaluation (question 3.17 of the MDS-UPDRS), MOCA, MDS-UPDRS III, H&Y rating, Drug, alcohol and tobacco abuse screening test, safety assessments (as listed in section IV A, except for RBDSQ, IRLS), EKG and safety labs (complete blood count, hemoglobin A1C, complete metabolic profile and urinalysis), blood cannabis analysis testing, serum pregnancy test (for women childbearing potential), and inclusion/exclusion criteria are done. Study subjects are instructed not to take cannabis from outside source throughout the study.

Visit 2-Baseline visit: Eligibility confirmation, medical history, and concomitant medications, formal drug interaction assessment, vital signs, orthostatic blood pressures, brief physical exam (heart and lung auscultation), MDS-UPDRS, UDysRS, and inclusion/exclusion criteria, RBDSQ, IRLS, C-SSRS, urine drug (THC) test (urine dipstick testing), urine pregnancy test (women childbearing potential), safety assessments, and drug and home diary dispensing are done. Subjects will take the first dose in clinic and will be monitored and vital signs (including orthostatic blood pressure and pulse) will be taken to check for study drug tolerability at 1 hour after taking the study drug. Subjects are instructed on how to take the medication and how to fill out the diary at home. To make sure the diary is recorded correctly, subjects will be asked to mail, email or fax a copy or image of the diary they filled out within 3 days of increasing from 5 to 7.5 mg/kg/day. This is so that diary errors can be corrected early. Subjects will be told not to take the study drug on the day of the next visit, as they will take it upon arrival under instruction by study staff. Subjects are also instructed to bring in empty, partially used and unused bottles of study drug at next clinical visit. Subjects will be given two urine cups, 100 mL each, and will be instructed to collect their urine the morning of the final assessment visit. They are asked to fill each cup at least 3/4 full, if possible, and to bring them to the visit (no refrigeration needed).

Visit 3-Final Assessment visit: Medical history and concomitant medications collection, formal drug interaction assessment, vital signs, orthostatic blood pressures, complete physical exam and detailed neurological exam, and all efficacy and safety assessments are repeated that were done in the screening, baseline and 20 mg/kg/day assessment visit, except for the cannabis, drug, alcohol and tobacco abuse questionnaire. Adverse event check is done. Subjects will take the study drug upon their arrival to the clinic and record the time. On the morning of the visit, subjects will collect their urine and bring it to the visit. Study coordinator will collect and store the urine cups in a -80°C freezer until shipment. Blood draw is performed 3 hours after the dose is taken, for cannabis testing and safety labs. Subjects will be monitored and vital signs and orthostatic blood pressures will be checked at 1 and 3 hours after taking the study drug. Returned study drug is counted. Compliance will be checked by study drug count and cannabis analysis testing. Home diary is collected and reviewed.

Visit 4-Safety follow up: Concomitant medications, formal drug interaction assessment, vital signs, orthostatic blood pressures, history & complete physical examination, MDS UPDRS, H&Y rating, UDysRS, MoCA, QUIP-RS, C-SSRS, NPI, SCOPA-sleep, RBDSQ, Anxiety short form, Depression short form, Emotional and behavioral dyscontrol short form, Fatigue Severity Scale, Pain Intensity and Interference short form, IRLS, adverse event check, blood cannabis lab testing and urine pregnancy test (women childbearing potential). Safety labs and EKG will be done if there was a clinically significant change at the assessment visit compared to baseline visit. The PI will evaluate the subject for signs of withdrawal.

